5.0 Special Considerations

5.1 Health Insurance Portability and Accountability Act (HIPAA)

HIPAA will be collected with consent.

5.2 Family Educational Rights and Privacy Act (FERPA)

N/A

5.3 NJ Access to Medical Research Act (Surrogate Consent)

N/A

5.4 General Data Protection Regulation (GDPR)

N/A

5.5 Code of Federal Regulations Title 45 Part 46 (Vulnerable Populations)

N/A

6.0 Data Management Plan

6.1 Data Analysis

Statistical comparisons will focus on individual and aggregate comparisons with respect to baseline to follow-up change in gut microbiota populations and biochemistry profile in blood and urine samples.

For each outcome, the equality of the outcome means for GP-SPI versus SPI will be tested against a two-directional alternative, controlling the type 1 error at $\alpha = 0.05$. The analyses will be conducted using t-tests for between group analysis and with repeated measures to conduct analysis of variance. Post-hoc tests will be conducted for pairwise comparisons of GP-SPI and SPI employing the Tukey method for controlling the global comparison-wise significance at 0.05 level. Logarithms or other transformations will be applied for data seriously deviating from normality; alternatively, non-parametric analyses may be conducted.

Handling of missing data: The data will be analyzed using the procedures PROC MIXED and PROC GLIMMIX SAS (v 9.3 or later). Thus, mixed effects models for repeated measures will be employed to analyze all available data irrespective of missing or incomplete data attributable to dropouts or other phenomena. In anticipation of the possibility of missing data, we plan to conduct sensitivity analyses that compare our findings against protocol completer analyses and last observation carried forward analyses in addition to investigating characteristics of participants who fail to protocol.

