After consent a participant ID will be assigned to subject. Demographics, medical history, height, and weight (**Demographics** and **Medical History** forms attached) will be recorded for each subject. Females will be given a urine-based pregnancy test onsite and result will be recorded. If inclusion criteria are met at this time, subject will be asked to schedule a visit at CAB with study nurses for a blood draw to perform CMP screening test. If CMP results are within normal range the subject will be enrolled and return to IFNH to receive study materials needed for participation in the study. If any CMP values are outside normal ranges subject will be advised that they do not fulfill all eligibility criteria, they will be given a copy of their CMP results, and if necessary, advised to see their primary care provider. All screened subjects will be documented on **Screening and Enrollment Log** (attached).

The final selection will be contingent upon the individuals meeting all eligibility criteria and deemed capable of complying with the study protocol.

Study Procedures

- Thirty subjects will be enrolled.
- **Food List:** Participants will maintain their usual diet except for a provided list of PAC-rich foods that they will be asked to abstain from for a 5-day wash-out period and during the 10-day intervention. The Food List is provided below. The goal is to have GP-SPI as the main/only source of PAC in the diet for the study period.
- **Wash-out and SPI (Day -5 through -1):** On day -5 (pre-baseline) before any supplementation, each subject will collect their fecal and urine sample. Each subject will then consume SPI twice a day (provided as pre-weighed packets of 20 g) during a 5-day wash-out period (days -5, -4, -3, -2, and -1). Subjects will be instructed to mix each packet of SPI in 250 mL of water or in a smoothie (recipe example below will be provided) using allowed foods as detailed in instructions and consume once in the morning before breakfast and once in the evening before dinner.

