- Carrot
- Celery
- Cucumber
- Eggplant
- Lettuce
- Onion
- Pepper
- Potato
- Radish
- Sweet potato
- Zucchini
- Beets

- Corn meal
- Tortilla chips
- Wheat
- Oats
- Rice
- Soybeans
- Navy beans
- Chick peas
- Macadamia nuts
- Pine nuts
- Brazil nuts

- White chocolate

- Basil
- Oregano
- Parsley
- Paprika
- Black pepper
- Mustard seeds
- Poppy seeds
- Garlic powder
- Ginger
- Onion powder
- Turmeric
- Cloves
- Chili powder

The following plant foods have low levels of proanthocyanidin compounds and may be consumed in moderation during the study period, meaning just 1 serving per day of any food from the list below.

- Pear (1 fruit)
- Nectarine (1 fruit)
- Cherries (10 cherries)
- Apricot (1 fruit)

- Kiwi (1 fruit)
- Avocado (1 fruit)
- Mango (1 fruit or 1 cup of sliced fruit)
- Banana (1 fruit)
- Persimmon (1 fruit)
- Pomegranate (1/4 cup kernels)

- Indian Squash (1 ounce or 28 g)
- Black beans (1 ounce or 28 g)
- Lentils (1 ounce or 28 g)

- Roasted peanuts (40 pieces = 1 ounce or 28 g)
- Peanut butter (1 tablespoon)
- Cashews (18 pieces = 1 ounce or 28 g)
- Chestnuts (8-10 kernels)

- Beer (1 can/bottle = 12 ounces)
- Apple juice (1 cup or 230 mL)
- Chocolate milk (1 cup or 230 mL)

A. Data Points

Data elements to be collected include: medical history, demographics, digital and written food diaries, adverse events, metabolomics data from blood and urine samples, microbiome data from fecal samples

B. Study Duration

It will take 2 years to complete this study. Each subject will participate for 17 days.

C. Endpoints

Primary endpoint:

- 1) Evaluate the effect of nutritional supplementation with GP-SPI on gut microbiota composition using 16S rRNA gene sequencing.

Secondary endpoints:

- 1) To evaluate the effect of GP-SPI on kidney and liver health/function (safety) via comprehensive metabolic panel (CMP).
- 2) Collect fecal, blood, and urine samples and store for a microbiome-wide association study (MWAS, funded by R01 AT010242-01).

Microbiome wide association study (MWAS)

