1.6 Study Variables

A. Independent Variables, Interventions, or Predictor Variables

The independent variables will be supplementation with SPI or GP-SPI.

B. Dependent Variables or Outcome Measures

Outcome measures are gut microbial community analyses, CMP results, urine and serum metabolites, and bacterial genes, species/strains.

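### The only inferential rule for the CMP safety endpoint is a test of equal means, which cannot by itself support a safety conclusion; counts of participants leaving the normal range should be pre-specified

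*Combined protocol and SAP*

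**What the plan says.** Section 1.3 (Endpoints) sets as a secondary endpoint "To evaluate the effect of GP-SPI on kidney and liver health/function (safety) via comprehensive metabolic panel (CMP"). Section 1.6 places the panel among the outcomes: "Outcome measures are gut microbial community analyses, CMP results, urine and serum metabolites, and bacterial genes, species/strains". Section 6.1 then states "For each outcome, the equality of the outcome means for GP-SPI versus SPI will be tested". The test is two-sided at the 0.05 level, by t-tests, repeated-measures ANOVA or mixed models, with transformation or a non-parametric method as fallback.

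Section 6.1 opens more broadly: "Statistical comparisons will focus on individual and aggregate comparisons with respect to baseline to follow-up change", covering the microbiota and the blood and urine biochemistry. It gives no rule for the individual part.

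Under section 1.8 the panel is measured at screening, day 0 (after five days of SPI) and day 11 (after ten days of GP-SPI). Normal ranges are used for entry: "If CMP results are within normal range the subject will be enrolled" (section 1.3, Eligibility Screening). No planned analysis uses them again. The documents give no margin, clinically important change, CMP variability or CMP power. The one sample size calculation (section 1.5) concerns *A. muciniphila* abundance.

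**The concern.** A test of equal means asks whether the group as a whole has moved. A safety endpoint also has to show whether a few people have moved a long way. A large rise in one or two participants shifts the mean little and inflates the SD in the denominator, so the test can become less likely to signal as the rise grows.

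Every participant enters with panel values in range, so a new out-of-range value is a natural and readily available individual measure. As written, the reported safety result could be a p-value that barely responds to such events, with nothing beside it to show how little a non-significant result rules out.

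**Working it through.** **Completers.** Section 4.3 gives 30 enrolled and 20% loss: 30 × (1 − 0.20) = 24, consistent with its 6 non-completers. A participant without a day 11 draw contributes no observed change.

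**Why the mean test is insensitive.** Let k of n = 24 participants rise by s, with change SD σ in everyone otherwise.
- Mean change = ks/n.
- Expected variance of changes = σ² + s²k(n − k)/[n(n − 1)].
- Example: k = 2, s = 5, σ = 1. Mean = 10/24 = 0.417. Variance = 1 + 25 × 2 × 22/(24 × 23) = 2.99. Standard error = √(2.99/24) = 0.353. Approximate t = 0.417/0.353 = 1.18. The critical value on 23 df is 2.07.
- As s grows without limit, t tends to √[k(n − 1)/(n − k)]: 1.00 for k = 1, √(46/22) = 1.45 for k = 2, √(69/21) = 1.81 for k = 3. All lie below 2.07, so a larger rise in these few people does not rescue the test.

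**Simulated power** (paired two-sided t-test at 0.05, n = 24). Assumed: rises of 3 or 5 between-person SDs; change SD 0.5 or 1.0 in the same units.

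| Participants affected | Significant in |
|---|---|
| 1 of 24 | about 1–5% of trials |
| 2 of 24 | about 3–8% |
| 3 of 24 | about 14–18% |

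With one person affected, the test signals no more often than its 5% false-positive rate. The non-parametric fallback does not help: a signed-rank test in the same settings is significant in 4–5%, 8% and 11–13% of trials.

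**Shift common to all.** At n = 24, 80% power needs a mean change of 0.60 SD of change. The 95% interval for the mean change has half-width 2.069/√24 = 0.42 SD.

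**What a count would show.**
- Upper limit for 0 of 24: 1 − 0.05^(1/24) = 11.7% one-sided; 1 − 0.025^(1/24) = 14.2% two-sided.
- Chance of at least one case: 1 − 0.95^24 = 71% at a true rate of 5%; 1 − 0.90^24 = 92% at 10%.

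**Chance excursions.** Assume 95% reference ranges, 10 to 14 independent analytes and a repeat correlation of 0.6 to 0.9. With no effect at all, 1.4% to 3.3% of values that were in range at both screening and day 0 leave the range at day 11.
- Any analyte: 24 × (1 − 0.986^10) = 3.2 participants, up to 24 × (1 − 0.967^14) = 9.0. Zero will rarely be seen in an overall count.
- One analyte: the chance of zero in 24 is 0.967^24 = 45% to 0.986^24 = 71%, so the zero-event limit is relevant there.

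**The case against.** Four points count on the other side.

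- **The plan does not announce an over-reading.** A reader might infer that a non-significant result will be reported as showing no effect on kidney and liver. The documents do not support that: nowhere do they plan such a statement. What remains is that nothing in section 6.1 guards against it.
- **Individual change is not ignored.** A reader might also infer that the plan looks only at means. Section 6.1 names individual comparisons of change from baseline, so the gap is narrower: they have no rule, threshold or summary.
- **Harm need not go unseen.** Participants receive their results and are encouraged to see a doctor if these are abnormal (section 4.7). A committee with a clinician and a biostatistician reviews safety, including adverse events (section 6.3). Its report form is an attachment not available here and may tabulate CMP abnormalities. These are oversight steps, however, and do not define what the endpoint reports.
- **Mean change is a legitimate part of the question.** The objective is the effect on kidney and liver function, and a mean change with its interval describes part of that. The documents also do not say how injury from a supplement would present; harm confined to a few people is an assumption here.

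The first three points limit what can be claimed, and the fourth is why mean change should stay as description. None supplies an individual-level summary of the endpoint.

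**Conclusion.** This is a cheap improvement to a secondary endpoint in a single-arm pilot, not a flaw in the design or the primary result. The mean test is the only inferential rule stated for the panel. With about 24 completers it is significant in roughly 1 to 18% of trials when 1 to 3 participants are affected, so taken alone it cannot support a safety conclusion.

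The power figures rest on the assumed rises and change SDs, because the documents give no CMP variability. The zero-event limits need only the number of participants assessed. They widen if fewer than 24 are in range at day 0 and measured at day 11.

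**What to change.** Add a short CMP paragraph to section 6.1:

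1. For each kidney and liver analyte, report the number of participants in range at day 0 and out of range at day 11, with exact 95% limits. Quote the upper limit when the count is zero.
2. Beside it, give the same count from screening to day 0 under SPI as comparator. Treat the comparison as descriptive: the periods differ in length and the order is fixed. With no effect, the screening-to-day-0 count would also tend to run slightly higher than a count among participants already in range twice.
3. If an overall any-analyte count is given, show it only with that comparator, because chance excursions are expected.
4. Keep mean change with its 95% interval as description, and state that a non-significant mean test is not evidence of no effect.

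The cost is one small table from data already collected at the three draws. The downside is presentational: a stated upper limit of 11.7% or 14.2% looks less favourable than a report of no significant change.

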1.3 Research Design and Methods

Overview

This is a pilot time course study to characterize the effect of GP-SPI on the gut (i.e. fecal) bacterial community of healthy subjects. Following screening, enrolled subjects will washout of PAC-rich foods for 5 days while also consuming SPI. Subjects will then consume GP-SPI over a 10-day supplementation period. Fecal, urine, and blood samples will be collected. Comprehensive metabolic panel (CMP) tests performed before and after the GP-SPI supplementation period will monitor liver and kidney health. Using deidentified fecal, urine, and blood samples collected from time course study a MWAS study (funded by R01 AT010242-01) will be performed.

Successful completion of this pilot study will yield data that will inform the design of a follow-up placebo-controlled intervention study, which will be described in a separate clinical protocol that will be submitted to IRB for approval.

A. Research Procedures

[figure not shown]

Figure 1. Clinical Study Design

Location

Screening and out-patient visits will take place in the Surgery Clinic in the Clinical Academic Building (CAB) or Surgery Department (MEB 5) and NJ Institute of Food Nutrition and Health (IFNH).

Recruitment

Prospective participants will be recruited through flyers posted locally on Rutgers University campuses and sent to university email lists (**Flyer** attached). Interested subjects will call in or email to receive further information about the study. A member of the study team will give a brief summary of the study. If the subject requests a screening appointment, the investigator will ask for verbal consent to proceed with a list

of questions (**Telephone Script** attached). Collecting this information at this time assists in expediting the paperwork during the visit and spares ineligible subjects the inconvenience of a futile appointment.

Eligibility Screening

At the screening visit (at IFNH), a member of the study team will explain the study in detail to the subject. Full explanation of study procedures and potential risks will be provided. The subject will have ample time to read the Consent and ask questions before signing and proceeding with screening procedures. A signed copy of Consent form (form attached) will be given to the subject.

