4) Statistical analysis: To find the bacteria that respond to GP either positively or negatively (i.e. GP responders) we will omit those strains that are found to change with only SPI supplementation. To further understand how the GP responders affect host metabolic health as a group, we will derive a GP Responder

Index (GRI) based on the abundance and diversity [Heip evenness] of the identified bacteria (36). Data will be subject to two-way repeated measures ANOVA to decipher main effects and interactions between GP and SPI. $P < 0.05$ will be considered significant.

To detect significant differences in metabolites MetaboAnalyst 3.0 software (<http://www.metaboanalyst.ca/>) will be used. Principal components analysis (PCA) will transform original data variables into a smaller number orthogonal variables built from linear combinations to explain most of the data variance and cluster samples from each time-point or group to be analyzed. Significant difference ($p < 0.05$) will be determined within subject at different time-points, within group, and between groups. Variable importance in projection (VIP) scores will be estimated to select metabolites biomarkers from a partial least squares-discriminant analysis (PLS-DA). VIP scores are a weighted sum of PLS weights for each variable and measure the contribution of each predictor variable to the PLS-DA model. Compounds with VIP score > 4 represent metabolites with greatest change, which will be chosen for proof of identity. Before carrying out PCA and PLS-DA analyses, peak intensity will be controlled by a logarithmic transformation, and monitored by Pareto scaling. Methods for data preprocessing and statistical analysis will be optimized and additional corrections and tools will be applied as needed (37; 38).

Co-inertia analysis: To aid interpretation of the relationship between the bacterial responders and metabolomics datasets, they will be integrated using a multivariate method known as co-inertia analysis (CIA) (39). We expect to uncover bacterial species/strain level increases and decreases in GP-SPI-supplemented subjects that correlate with a concomitant increase and decrease in production of their metabolites.

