1.5 Sample Size Justification

Using conservative estimates for mean relative abundance (RA) of *A. muciniphila* in human subjects (i.e. baseline mean RA of 0.1% increasing to 0.4% on day 10 with standard deviation of 0.5%), a sample size of 16 subjects would be required to detect significant difference from baseline levels (target power = 95%, actual power = 96.2%; $\alpha = 0.05$, Hotelling-Lawley Trace test for repeated measures, GLIMMPSE).

16S rRNA gene sequencing data will be compared longitudinally within each subject and in aggregate and consists of surveying the relative composition of gut microbiota populations in fecal samples and mine data for differences in phyla (e.g. *Bacteroidetes* vs. *Firmicutes*), genera, and specific microbes (*Akkermansia* spp.) as far as resolution allows. Power calculations will be performed using data obtained from this pilot time course study to assist in finalizing design of a future randomized, placebo-controlled intervention study.

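### Section 6.1 plans between-group t-tests and the MWAS section a GP-by-SPI interaction, but one group takes SPI then GP-SPI; neither fits, and the primary within-subject analysis is not named

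*Combined protocol and SAP*

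**What the plan says.** **Design.** The overview in section 1.3 reads: "enrolled subjects will washout of PAC-rich foods for 5 days while also consuming SPI. Subjects will then consume GP-SPI over a 10-day supplementation period". The order is fixed and there is no parallel arm; a placebo-controlled study is left to a later protocol. Stool is sampled on day -5 (before any supplement), on day 0 (after the SPI days) and on days 2, 4, 6, 8 and 10 of GP-SPI. During the study, blood is drawn on days 0 and 11 only.

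**Analysis, section 6.1.** For each outcome, "the equality of the outcome means for GP-SPI versus SPI will be tested against a two-directional alternative". The tests are then named: "The analyses will be conducted using t-tests for between group analysis and with repeated measures to conduct analysis of variance". Next comes "Post-hoc tests will be conducted for pairwise comparisons of GP-SPI and SPI employing the Tukey method", with a 0.05 level. The paragraph on missing data adds mixed models for repeated measures (PROC MIXED, PROC GLIMMIX) applied to all available data.

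**Analysis, section 1.3, MWAS, item 4.** "Data will be subject to two-way repeated measures ANOVA to decipher main effects and interactions between GP and SPI". The metabolite paragraph there also mentions differences between groups.

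**Sample size, section 1.5.** Sixteen subjects are "required to detect significant difference from baseline levels", with 96.2% power from a repeated-measures Hotelling-Lawley test.

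**The concern.** SPI and GP-SPI are consecutive periods in the same people, so a between-group comparison has no groups to compare. An analyst who takes the wording literally would run an independent-samples t-test on paired data and lose the within-subject precision on which section 1.5 sized the study. An analyst who starts from the mixed-model sentence would run something quite different. The text does not rank the two and does not define a time factor, a reference day or a contrast, so the same data could yield two answers for the primary endpoint.

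The MWAS analysis has a different defect. A two-factor model with interaction needs information from all four combinations of GP and SPI, and this design cannot supply one of them.

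**Working it through.** **Inputs.** Section 1.5: mean 0.1% rising to 0.4%, so a difference of 0.3; SD 0.5; alpha 0.05; n=16; power 96.2%. Section 4.3: 30 enrolled with 20% loss, so 30 × 0.8 = 24 completers. The within-subject correlation (rho) is not given; 0.3 to 0.82 is assumed below.

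**1. The plan's own figure.** Without rho or the means on intermediate days, 96.2% cannot be reproduced from the stated inputs alone. Two readings can be tested.
- Unpaired: n per group for 95% power = 2 × (1.960 + 1.645)² × 0.5² / 0.3² = 72.2, so 73. With 16 per group, power is 38%. This reading does not give 96.2%.
- Paired, day 0 against day 10: SD of the change = 0.5 × √(2(1 − rho)). At rho = 0.82 this is 0.300, the noncentrality is 0.3/0.300 × √16 = 4.0, the critical t on 15 df is 2.131, and power is 96.2%. With n=15 it is 94.9%.

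A Hotelling test over six or seven time points with equal correlations returns 96.2% at rho of about 0.80 to 0.88, depending on the assumed trajectory. The stated power therefore belongs to a within-subject analysis with a high correlation.

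**2. What the unpaired test does to these data.** It uses a standard error of 0.5 × √(2/n), whereas the true one is 0.5 × √(2(1 − rho)/n). The ratio is 1/√(1 − rho), which is 2.36 at rho = 0.82. At n=16 it needs an observed difference of roughly 2.042 × 0.177 = 0.36 for significance, more than the assumed 0.3.

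Paired power below is from the noncentral t. Unpaired power and type I error are from 60,000 simulated bivariate-normal data sets per setting.

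| rho | n=16 unpaired | n=16 paired | n=24 unpaired | n=24 paired | Type I error, unpaired |
|---|---|---|---|---|---|
| 0.3 | 36% | 47.5% | 54% | 66.3% | about 0.02 |
| 0.5 | 34% | 61.2% | 54% | 80.4% | about 0.007 |
| 0.7 | 31% | 82.5% | 56% | 95.3% | about 0.001 |
| 0.82 | 28% | 96.2% | 57% | 99.7% | about 0.0001 |

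The error is in the conservative direction: power is lost and false positives are not created.

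**3. The interaction.** Code SPI and GP as 0/1 over the seven stool days.

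| Days | SPI | GP | SPI × GP |
|---|---|---|---|
| -5 | 0 | 0 | 0 |
| 0 | 1 | 0 | 0 |
| 2, 4, 6, 8, 10 | 1 | 1 | 1 |

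The GP column equals the SPI × GP column in every row. Intercept, SPI, GP and interaction are four columns of rank 3. Section 6.3.C explains why: the polyphenols are sorbed to SPI, so GP without SPI never occurs. Adding GP and SPI to seven day effects leaves the rank at 7, so even the main effects are before-after contrasts between days.

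**4. Tukey.** With two levels (SPI, GP-SPI) the Tukey critical value on 23 df is 2.069, the ordinary t value, so nothing is adjusted. With the seven days as levels it is about 3.0 to 3.2, depending on the error df, so it does adjust. Section 6.1 does not define the factor.

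**The case against.** The strongest reply is that a within-subject analysis is already planned. Section 6.1 opens with change from baseline to follow-up, the sentence with the t-tests also names repeated-measures ANOVA, and the mixed-model statement covers all available data although it sits under missing data. Nothing there says independent or unpaired. This largely stands. The defect is confined to the t-test wording and to the missing statement of which analysis is primary.

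A reader might infer several stronger things that the documents do not support:
- **That the trial has about 28% power, or a type I error of 0.0001.** This holds only if an unpaired t-test is the analysis relied on and rho is 0.82, a value solved backwards from two time points. It also assumes normality, and a normal distribution with mean 0.1 and SD 0.5 puts 42% of baseline relative abundances below zero.
- **That the Tukey step does nothing and the GP-SPI days are uncontrolled.** This needs a two-level factor. Section 6.1 speaks of pairwise comparisons in the plural and of "employing the Tukey method for controlling the global comparison-wise significance at 0.05 level"; with day as the factor there is an adjustment.
- **That the inestimable interaction undermines the primary endpoint.** It appears only in the MWAS part, next to the GP Responder Index, and not in section 6.1.

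It is also fair to say that this is a pilot. That lowers the stakes, but section 1.5 intends to use its data to power the next trial.

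**Conclusion.** The point holds in limited form. Two stated analyses do not fit a single-group, fixed-order design: the between-group t-tests and the GP-by-SPI interaction.

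For the t-tests, the cost depends on the unknown correlation. From rho 0.3 to 0.82, reading them as independent-samples tests gives up about 12 to 68 percentage points of power at n=16 (47.5 − 36; 96.2 − 28) and about 12 to 43 at 24 completers (66.3 − 54; 99.7 − 57). These figures rest on the section 1.5 difference and SD and on normality. The repeated-measures ANOVA and mixed models do not share this loss if subject is the repeated unit, so the gap to close is that none is named as primary with a defined contrast.

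The interaction finding needs no assumption: one of four cells is empty, and no software or covariance choice changes that. Correcting both items should be done before analysis. It does not alter the fact that day 10 against day 0 remains a before-after comparison.

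**What to change.** **Section 6.1**
- Replace the between-group t-test with within-subject analysis.
- Name the already planned mixed model as primary: day (-5, 0, 2, 4, 6, 8, 10) as a categorical factor and repeated measures within subject. Fix the covariance structure in advance; an unstructured matrix has 7 × 8 / 2 = 28 parameters for about 24 completers.
- Define the primary contrast as day 10 minus day 0, two-sided at 0.05.
- State that the multiplicity adjustment is applied across days. Tukey or Dunnett would both serve.
- Report day 0 minus day -5 separately, as the combined change with SPI and washout.
- For CMP and serum outcomes, which have no day 10 sample, use a paired day 11 versus day 0 comparison. Without this line the blood outcomes would have no stated test.

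**Section 1.3, MWAS, item 4**
- Replace the two-way GP-by-SPI ANOVA with a one-factor repeated-measures model (none, SPI, GP-SPI; or day). Drop the interaction and the between-groups wording.

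**Cost.** Wording only. The samples, visits and software are already in the plan, and enrolment does not change.
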